#### **Risks of Xenon Inhalation**

Inhalation of hyperpolarized  $^{129}\text{Xe}$  may carry some minor risks. Xenon is a general anesthetic when breathed continuously at concentrations greater than 70% for extended periods of time. In the proposed study, xenon will be delivered in a single breath, with alveolar concentrations below 25%. At these concentrations, subjects may experience transient effects including dizziness, slight tingling or numbness of the extremities, nausea, smelling of flowers, or a feeling of well-being and euphoria. These effects will wane within 1-2 minutes of exhaling the xenon and are documented in the consent forms.

A second risk comes from administering HP 129Xe without oxygen. This is necessary to preserve good image quality, because O2 is paramagnetic and depolarizes the HP 129Xe. Administration of a single anoxic 1-liter breath has been well tolerated by subjects undergoing both 3He and 129Xe MRI because for a single breath, the residual oxygen in the subject's lungs is sufficient to maintain blood O2 saturation during the breath-hold. If a subject has an oxygen saturation below 90% at baseline, the attending medical professional may provide supplemental oxygen via nasal cannula as needed. Numerous studies have now been published demonstrating the safety and tolerability of hyperpolarized 129Xe MRI.

Hyperpolarized 129Xe is treated as a drug by the FDA and is covered by our existing Investigational New Drug Filing (IND# 109,490), which has been active for 7 years and has reported no SAEs, and no early withdrawals from the study. The proposed studies will use hyperpolarized 129Xe prepared in exact accordance with the Drug Master File that is part of the IND held by Polarean, Inc. Our center has been granted the rights by Polarean to cross-reference this IND for their own filings. We will continue to follow a 129Xe administration protocol that is well established in our hands.

### **Risks of Incidental Findings**

Since the MRI methods being tested are experimental, the MRI images will not be formally reviewed for incidental findings. However, if there is something that is of concern to the PI, then the PI will approach the IRB for guidance on how to proceed on a case-by-case basis. The consent will clearly state that the MRI images will not be evaluated for incidental imaging findings.

**Protection Against Risk:** Study visits and informed consent will be performed in private rooms, to prevent potential loss of confidentiality. This individual will be present in the MRI suite during 129Xe administration and will monitor all aspects of the subject's wellbeing and record any transient CNS effects and adverse events should they occur. The subject will be monitored continuously by an MRI-compatible pulse oximeter, recording both heart rate and oxygen saturation. Subjects may discontinue the study at any time. The MRI suite is also equipped with a safe source of supplemental oxygen that can be provided if needed for patients with pulmonary disease to maintain O2 saturation. All subjects will receive a 24-hour follow-up phone call to check for any symptoms or adverse effects. Any symptoms or effects will be recorded, regardless of their suspected association with 129Xe MRI.

Extraordinary care will be taken to ensure that all patient data remains confidential and any information is deidentified prior to publication or presentation. All study personnel will have completed their institution's mandatory training in human subjects' research and protecting PHI.

### **Potential Benefits to Subjects:**

We anticipate no direct benefit to subjects as a result of participating in the study, since our primary emphasis is to collect a range of MR images and develop interpretation of these results over time. However, it is conceivable that either the anatomical 1H scans or 129Xe MR scans may reveal an incidental pathology that requires medical attention. Such a finding could benefit the subject because it will be found earlier than would likely be the case during the subject's normal medical care. Any such findings will be immediately communicated to the subject and his/her physician and all associated records of the study will be made available to them for any further work-ups. The potential benefit of this research is in the noninvasive diagnosis of PAH, which would obviate the need for invasive RHC in these patients.

### **Costs to the Subject:**

There are no additional costs to the subject for the MRI examination. Subjects will be compensated \$150.00 for the study visit.

### **Data Analysis & Statistical Considerations:**

We will perform pairwise comparisons for all endpoints before and after treatment with iTRE with correction for multiple comparisons. We will also compare the baseline and post-treatment values to a group of normal subjects so we can assess the degree of normalization of gas transfer associated with drug treatment.

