**Background & Significance:**

Pulmonary hypertension (PAH) carries a significant economic burden, with average annual health care costs of ~ \$100,000/yr. The diagnosis of PAH can be challenging, as it requires fulfillment of specific clinical and hemodynamic criteria. However, these are limited because they do not allow the diagnosis of PAH in the setting of concomitant left heart disease or lung disease. Patients with mild to moderate idiopathic pulmonary fibrosis (IPF) or chronic obstructive pulmonary disease (COPD), which are common in older patients, technically cannot be diagnosed with true PAH, but are diagnosed with Pulmonary Hypertension (PH). Similarly, hemodynamic criteria are limited by arbitrary cutoffs for mean pulmonary artery pressure (mPAP), pulmonary capillary wedge pressure (PCWP), and pulmonary vascular resistance (PVR) obtained at right heart catheterization (RHC) (PH is defined as mPAP  $\geq$  25 mmHg; PAH is defined as mPAP  $\geq$  25-mmHg and a PCWP  $\leq$  15 mmHg, with some criteria recommending an additional cutoff of PVR  $\geq$  3 Woods units. Moreover, it is currently unclear what constitutes abnormal hemodynamics in the setting of in lung disease, which can increase the PVR. These hemodynamic criteria also frequently exclude patients who may have a borderline elevation in mPAP or abnormalities primarily associated with exercise that are not captured with a resting heart catheterization. As the majority of patients who are now evaluated for PAH are older with common cardiac and pulmonary comorbidities, the clinical and hemodynamic criteria are frequently inadequate for diagnosing patients who actually have PVD.

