### **Design & Procedures:**

This study will consent 15 patients (accrued 12 subjects total) with pulmonary hypertension (PH). Patients will be on inhaled treprostinil (iTRE) as standard of care for their PH. Inhaled treprostinil (iTRE) is an FDA approved medication under the brand name of Tyvaso. The major pharmacologic actions of treprostinil are direct vasodilation of pulmonary and systemic arterial vascular beds and inhibition of platelet aggregation. The medication is delivered noninvasively, directly to the lungs using the approved ultrasonic nebulizer delivery system. Patients will take the inhaled treatment four times a day, about every four hours.

Patients will be characterized by their Xe MRI imaging, peripheral vasodilation and serum treprostinil concentration before and after treatment with iTRE. As iTRE has a plasma concentration half-life of ~ 45 minutes and time-to-peak concentration of 15 minutes, imaging will be conducted immediately before, 15 minutes after and 2-4 hours after drug treatment. This would potentially allow the visualization of changes in gas diffusion and peripheral vasodilation associated with iTRE. This is similar to changes seen in ventilation in asthma after treatment with bronchodilators. A follow-up scan at the 2-4hr time point would also allow us to test whether vasodilation persists in the lung vasculature compared to the peripheral circulation. This study seeks to deploy several forms of Xe MRI contrast. Specifically, the Xe MRI scans will provide 3D images of ventilation and gas exchange, and spectroscopic indices will be evaluated to test gas exchange dynamics with high temporal resolution. This will be augmented with several conventional H MRI scans to delineate the subject's thoracic cavity.

Once the subjects has signed consent, the study session will begin with a collection of relevant patient history and symptoms, measurement of hemoglobin levels (finger sensor), and urine pregnancy testing (if applicable). Study team will use the PFTs that are available from the medical record. Subjects will receive an IV catheter to be used for blood draws. The following activities will take place for the MRI procedure:

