1. Patient receives first scan before scheduled dose of iTRE (trough study) Baseline timepoint: Xe calibration and dissolved-phase spectroscopy - to obtain global RBC:barrier ratios, RBC oxygenation shifts, and spectral linewidths; Isotropic 3D Xe gas exchange MRI – to detect focal defects in gas transfer from airspaces to RBCs in capillary bed; Other H scans to obtain anatomic data on the lung.
2. Assessment of peripheral vasodilation in the arm and hands with noninvasive laser speckle imaging
3. Blood sample for serum treprostinil concentration
4. Subject takes iTRE treatment as with standard of care. Timepoint 1: Wait ~ 15 minutes to peak effect (peak study). Patient receives second scan: Xe calibration and dissolved-phase spectroscopy - to obtain global RBC:barrier ratios, RBC oxygenation shifts, and spectral linewidths; Isotropic 3D Xe gas exchange MRI – to detect focal defects in gas transfer from airspaces to RBCs in capillary bed; Other H scans to obtain anatomic data on the lung.

5. Assessment of peripheral vasodilation in the arm and hands with noninvasive laser speckle imaging
6. Blood sample for serum treprostinil concentration
7. Timepoint 2: 2-4 hrs after initial treatment with iTRE; Patient receives third scan:  $^{129}\text{Xe}$  calibration and dissolved-phase spectroscopy - to obtain global RBC:barrier ratios, RBC oxygenation shifts, and spectral linewidths; Isotropic 3D  $^{129}\text{Xe}$  gas exchange MRI – to detect focal defects in gas transfer from airspaces to RBCs in capillary bed; Other  $^1\text{H}$  scans to obtain anatomic data on the lung.
8. Assessment of peripheral vasodilation in the arm and hands with noninvasive laser speckle imaging
9. Blood sample for serum treprostinil concentration

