### **Selection of Subjects:**

We propose to recruit and consent 15 subjects (accrued 12 subjects total) with known PH on treatment with iTRE that are followed in the Duke Pulmonary Vascular Disease Clinic. Inclusion criteria includes: PH (mPAP  $\geq 25$  mmHg, PCWP  $\leq 15$  mmHg in the absence of significant concomitant left heart disease or lung disease), , maintenance on a stable, well-tolerated treatment dose of iTRE (ideally  $\geq 8$  breaths QID). Pregnant women will be excluded from this study. Women of childbearing potential must have a negative urine pregnancy test in order to participate on this study.

Definition of Women of CBP: The median age of menopause in the US, defined as 12 months of amenorrhea, is 51 years; by age 48, approximately 15% of women will be postmenopausal, while virtually 100% will be post-menopausal by age 55. Women are considered past the age of “child-bearing potential” if they are greater than 55 years of age, OR they are at least 50 years of age AND o have not menstruated for at least 12 months, OR have a documented Follicle Stimulating Hormone (FSH) level of greater than 40 mIU/mL. they are at least 45 years of age AND o have not menstruated for at least 18 months, OR o have a documented Follicle Stimulating Hormone (FSH) level of greater than 40 mIU/mL. For drugs classified, or likely to be classified, as FDA Category X, the duration of amenorrhea for women of all ages must be 24 months, consistent with FDA labeling of these drugs.

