### **Statistical Plan**

We will perform pairwise comparisons for all endpoints before and after treatment with Tyvaso with correction for multiple comparisons. We will also compare the baseline and post-treatment values to a group of normal subjects so we can assess the degree of normalization of gas transfer associated with drug treatment.

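### Does comparing patients with an unspecified group of normal subjects make the planned assessment of normalization unsound?

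*Combined protocol and SAP*

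**What the plan says.** The statistical text consists of two sentences, given under Data Analysis & Statistical Considerations and repeated almost word for word under Statistical Plan. The first sets out the main analysis: "We will perform pairwise comparisons for all endpoints before and after treatment with iTRE with correction for multiple comparisons". The second adds the reference group: "We will also compare the baseline and post-treatment values to a group of normal subjects so we can assess the degree of normalization". In the Statistical Plan version the investigators will "compare the baseline and post-treatment values to a group of normal subjects so we can assess the degree of normalization of gas transfer".

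Selection of Subjects describes patients only: "We propose to recruit and consent 15 subjects (accrued 12 subjects total) with known PH on treatment with iTRE". Neither that section nor Design & Procedures recruits or schedules normal subjects, so the normals presumably come from outside this protocol. That is an inference. Background & Significance mentions earlier volunteers scanned at the centre but does not name them as the reference group.

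Design & Procedures states that "imaging will be conducted immediately before, 15 minutes after and 2-4 hours after drug treatment". There are therefore two post-dose scans, and the statistical text does not say which is compared with normal.

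No test against the normals, margin, significance level or measure of normalization is given. Nowhere does the document say that a non-significant difference from normal will be taken as normality.

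**The concern.** Two separate comparisons with one reference group invite a familiar error: patients differ from normal at trough, no longer differ after the dose, and are declared normalized. With 12 patients, failing to find a difference says little about whether one exists, so a partial recovery could be presented as a full one.

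The reference group could also mislead by itself. Background & Significance says of the wider population: "As the majority of patients who are now evaluated for PAH are older with common cardiac and pulmonary comorbidities". If the normals were much younger, or scanned by another method, part of the baseline gap would reflect age or technique rather than disease.

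At stake is the secondary statement about how far gas transfer returns toward normal. The stated purpose, detecting improvement within patients, does not depend on it.

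**Working it through.** The plan gives no power, SD, effect size or sample-size derivation, so there is no figure to reproduce. The only documented input is 12 patients (15 consented). Everything else below is assumed: 12 or 30 normals, SD 1 in both groups, correlation 0.7-0.9 between a patient's trough and post-dose values, two-sided 0.05 without correction, and pooled two-sample t tests against the same normals. Simulated figures use 40,000 runs per case.

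**1. How often the misleading pattern would arise if the two comparisons were used as tests.** Pattern: p < 0.05 at trough and p ≥ 0.05 post-dose. Ranges cover both numbers of normals and both correlations.

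| Trough deficit | True recovery | Pattern | Pattern with paired test also non-significant |
|---|---|---|---|
| 1 SD | none | 4-8% | – |
| 1 SD | 30% | 27-31% | 8-18% |
| 1 SD | 50% | 43-52% | – |
| 1.5 SD | 30% | 14-25% | 1-10% |
| 2 SD | 30% | 2-9% | at most 1.5% |
| 2.5 SD | 30% | under 2% | – |

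A multiplicity correction of the paired test would raise the last column. The pattern would be a poor measure of degree at a deficit near 1 SD and, with 30% recovery, would matter little at 2 SD or more. The documents do not say where this trial lies.

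**2. Precision of the remaining gap.** Half-width = t(0.975, 10 + m) × √(1/12 + 1/m), with m normals.

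- m = 12: 2.074 × √(1/12 + 1/12) = 2.074 × 0.408 = 0.85 SD
- m = 30: 2.021 × √(1/12 + 1/30) = 2.021 × 0.342 = 0.69 SD

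**3. Precision of the planned paired change.** Half-width = t(0.975, 11) × √(2(1 − ρ)/12).

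- ρ = 0.7: 2.201 × 0.224 = 0.49 SD
- ρ = 0.9: 2.201 × 0.129 = 0.28 SD

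Under these assumptions the paired analysis is the more precise of the two, and it needs no normals.

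**4. Whether an interval for the gap would correct the misreading.** Among trials showing the pattern, this is the share whose 95% interval still reaches at least half the original deficit:

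| Deficit | True recovery | 12 normals | 30 normals |
|---|---|---|---|
| 1 SD | 30% | over 99% | over 99% |
| 1 SD | 100% | 92-95% | 80-83% |
| 1.5 SD | 100% | 61% | 42-43% |

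At 1 SD the interval gives nearly the same warning whether recovery is 30% or complete, especially with 12 normals. It shows that the data are imprecise; it does not identify a false claim of normalization.

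**5. Age and sex.** If an offset of 0.5 SD existed with no disease deficit, the trough comparison would be significant in 22% (12 normals) to 30% (30 normals) of trials; for 0.3 SD, 11-14%. No such offset is documented. The sentence about older patients concerns people evaluated for PAH in general, not the 12 enrolled.

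**The case for a change.** The strongest case for a change is that a degree is a quantity, yet the plan names no estimate, interval, reference group or time point for it. A reader cannot tell what will be reported, and two p-values are an obvious way to carry out the sentence. A true remaining gap of 0.5 SD would be missed 70-78% of the time with 12 to 30 normals, and even 1000 normals would give only 41% power. Nor is the paired test a complete guard: at a 1 SD deficit with 30% recovery, the pattern appears without a significant paired change in 8-18% of trials. The remedy would need only wording and existing normal scans.

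The omissions are real, and the warning against reading non-significance as normality is sound statistics. But every pattern rate rests on a decision rule that the plan does not contain. Where the paired change is significant as well, the error would be overstating the size of a real improvement, not inventing one. The proposed interval adds no precision and, near a 1 SD deficit, does little to tell partial from full recovery.

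**Conclusion.** The concern does not call for a change. The text leaves open who the normals are, which post-dose scan is compared with them, and how the degree is expressed. Followed as written, the comparison can still be sound: patient values at each scan shown beside those of comparable normals, read together with the paired change. An analyst would ordinarily choose normals scanned and processed in the same way, report both post-dose scans, and not treat a non-significant gap as proof of normality. Nothing in the plan prevents this.

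The possible harm is confined to a secondary description in a 12-patient imaging study. Under the assumed inputs, a test-based misreading with 30% recovery would occur in 27-31% of trials at a 1 SD deficit and in 2-9% at 2 SD, but only if the investigators adopted a rule the plan does not state. The conclusion rests on the ordinary meaning of the plan's wording and on the absence of any documented age, sex or scan mismatch. A report that did claim normalization from a non-significant gap would deserve criticism then.

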### **Data & Safety Monitoring:**

All of the protocols in this proposal trial will be approved by Institutional Review Boards and reviewed periodically (every 12 months). Any adverse event will be reported to the appropriate IRB, the NIH Office of Biotechnology Activities (OBA), and if deemed related to xenon, will also be reported to FDA. Per Institutional and FDA policy, any serious adverse events (SAEs) will be reported within 24 hours. An annual progress report (or more frequently, if requested) will be submitted to the IRB, OBA and FDA.

The clinical investigator(s) will terminate the study immediately if the occurrence of serious adverse events that suggests unacceptable risk to the health of the subjects. All observed or volunteered adverse events, regardless of suspected causal relationship to the study procedure(s), will be recorded on the adverse events page(s) of the CRFs or worksheets. Events involving adverse experiences occurring during the study procedure(s) will be recorded.

Subjects will be monitored before, during, and after each dose of xenon to assess for adverse events and changes in vital signs. The parameters monitored include the following: subject assessment of anesthetic/analgesic effects, heart rate, and SpO2. The subjective sense of analgesia is assessed by inquiring about how the subject feels after administration of the Xenon dose. The subject will be asked to describe how they feel as well as about specific symptoms including: dizziness, light-headedness, numbness, euphoria, sleepiness, and tingling in extremities. SpO2 is measured at baseline and after each Xenon dose. A decrease of SpO2 by greater than 5% is considered significant. If the subject is to receive another dose, the next dose will not be administered until the SpO2 is within 5 % of its baseline value. If the subject has received their last dose, they will be observed until the SpO2 is within 5% of its baseline value or until the end of the observation period, whichever is longer. The subject will be monitored for the duration of the Xenon dose and post-procedural period, as well as the MRI with contrast by a qualified medical professional.

### **Privacy, Data Storage & Confidentiality:**

All consent and case report forms will be stored in a locked filing cabinet in the office of the study coordinator or principal investigator. Any other digital data (images, image analysis) will be associated only with the subject identification number and the date and time of the MRI. Image data will be retrieved and analyzed only by study personnel. Data will be captured in a RedCap database. After all manuscripts have been published the key to the code will be destroyed.

### **Statistical Plan**

We will perform pairwise comparisons for all endpoints before and after treatment with Tyvaso with correction for multiple comparisons. We will also compare the baseline and post-treatment values to a group of normal subjects so we can assess the degree of normalization of gas transfer associated with drug treatment.
